The diagnosis of AMI is confirmed by electrocardiographic changes indicative of new or presumed new ischemia (new ST-T wave changes), detection of elevated cardiac biomarkers or angiographic findings of an infarct related artery on coronary angiogram in the presence of ischemic symptoms.

Cardiogenic shock is defined as the presence of at least two of the following:

1. Hypotension (systolic blood pressure ≤ 90 mm Hg, or inotropes/vasopressors to maintain systolic blood pressure ≥ 90 mmHg)
2. Signs of end organ hypoperfusion (cool extremities, oliguria or anuria, or elevated lactate levels)
3. Hemodynamic criteria represented by a cardiac index of < 2.2 L/min/m² or a cardiac power output ≤ 0.6 watts.

2. Access, Baseline Invasive Hemodynamics

Due to the heterogeneous cohort of patients who present with AMICS, any diagnostic steps to ensure the presence of AMI or CS are left to the discretion of the primary operator (ie: timing of right heart catheterization, coronary angiogram and placement of MCS). We do recommend obtaining femoral access to ensure adequate vessel size for MCS. If a right heart catheterization has not been performed prior to MCS placement we recommend measuring a LVEDP prior to placement of MCS. In the event a LVEDP ≤ 15 mmHg, an alternate diagnosis should be suspected and right heart catheterization should be performed prior to MCS to confirm presence of cardiogenic shock. Following placement of large-bore access and administration of systemic anticoagulation an Impella catheter will be inserted and manipulated to obtain maximum

forward flow. Right heart catheterization (RHC) will be performed for calculation of cardiac power output (CPO), SVR and PCWP/RA ratio and pulmonary artery pulsatility index (PAPi), during the index procedure.

3. Intervention

PCI of the culprit lesion(s) should be performed, per national recommendations. We recommend against non-culprit PCI unless flow is impaired in the involved artery (ie. less than TIMI 3 flow and excluding chronic total occlusions); however the ultimate decision of multi-vessel PCI lies with primary operator. PCI can be performed with thrombectomy if a heavy thrombus burden is present. Once appropriately sized stents have been implanted angiography will be performed to assess TIMI flow. If TIMI III flow is not present, intracoronary vasodilatory should be administered at the discretion of the primary operator.

Prior to discharge from the cath lab, a formal neurovascular check should be performed for assessment of Impella-related limb ischemia. This can be performed either by an in-depth physical examination, peripheral angiogram, or lower extremities doppler studies. If signs of limb ischemia are noted, the peel-away sheath should be removed (if not already done so) with reassessment. If limb ischemia persists, antegrade access should be performed to provide distal lower extremity blood flow.

4. Post-PCI Hemodynamics

After the intervention is completed, right heart pressures, cardiac output, and CPO will be obtained. If CPO is > 0.6 , no further intervention is required. If CPO is ≤ 0.6 , right heart pressure will be reviewed to identify evidence of right ventricular failure if present (PAPi < 0.9).

If evidence of right ventricular failure are present (PAPi < 0.9), or if the Impella is suctioning, operators should consider right ventricular support with commercially available devices (Impella or Tandem Heart). Irrespective of CPO, evidence of RV shock is a warning not

to increase alpha agonists. These agents dramatically increase pulmonary vascular resistance (PVR) at a time of minimal RV reserve and can cause a lethal spiral as increasing doses of alpha agonists to maintain arterial pressure leads to decrease forward RV flow and worsens hypotension.

If CPO < 0.6 persists and RV shock is not the cause, consideration for the placement of an Impella 5.0 or a durable left ventricular assist device (LVAD) should be considered.

5. Weaning and Explantation

Impella devices should only be considered for explantation once the following criteria have been met:

1. Weaning of all inotropes and vasopressors
2. CPO > 0.6 watts without vasopressors or inotropes, and
3. PAPI > 0.9.

6. Safety and Monitoring

Cautious attention should be paid to the infrequent yet serious complication of limb ischemia with the use of large bore sheaths and devices. Detailed neurovascular checks should be performed while on Impella support. Use of antegrade sheaths to provide flow to the affected limb is strongly recommended in such cases. Prophylactic use antegrade access may also be considered, especially in patients who will likely require >24 hours of support. Although rare hemolysis can also occur, daily hemoglobin level should be obtained while on support. If there are signs of hematuria, Impella positioning should be checked via echocardiography.

NATIONAL CARADIOGENIC SHOCK INITIATIVE ALGORITHM

INCLUSION CRITERIA

- Acute Myocardial Infarction: STEMI or NSTEMI
 - Ischemic Symptoms
 - EKG and/or biomarker evidence of AMI (STEMI or NSTEMI)
- Cardiogenic Shock
 - Hypotension (<90/60) or the need for vasopressors or inotropes to maintain systolic blood pressure >90
 - Evidence of end organ hypoperfusion (cool extremities, oliguria, lactic acidosis)

EXCLUSION CRITERIA

- Evidence of Anoxic Brain Injury
- Unwitnessed out of hospital cardiac arrest or any cardiac arrest in which ROSC is not achieved in 30 minutes
- IABP placed prior to Impella
- Septic, anaphylactic, hemorrhagic, and neurologic causes of shock
- Non-ischemic causes of shock/hypotension (Pulmonary Embolism, Pneumothorax, Myocarditis, Tamponade, etc.)
- Active Bleeding
- Recent major surgery
- Mechanical Complications of AMI
- Known left ventricular thrombus
- Patient who did not receive revascularization
- Contraindication to intravenous systemic anticoagulation
- Mechanical aortic valve

ACTIVATE CATH LAB

ACCESS & HEMODYNAMIC SUPPORT

- Obtain femoral arterial access (via direct visualization with use of ultrasound and fluoro)
- Obtain venous access (Femoral or Internal Jugular)
- Obtain either Fick calculated cardiac index or LVEDP

IF LVEDP >15 or Cardiac Index < 2.2 AND anatomy suitable, place IMPELLA

Coronary Angiography & PCI

- Attempt to provide TIMI III flow in all major epicardial vessels other than CTO
- If unable to obtain TIMI III flow, consider administration of intra-coronary vasodilators

Perform Post-PCI Hemodynamic Calculations

- Cardiac Power Output (CPO): $\frac{MAP \times CO}{451}$
- Pulmonary Artery Pulsatility Index (PAPI): $\frac{sPAP - dPAP}{RA}$

Wean OFF Vasopressors and Inotropes

If CPO is >0.6 and PAPI >0.9, operators should wean vasopressors and inotropes and determine if Impella can be weaned and removed in the Cath Lab or left in place with transfer to ICU.

Escalation of Support

If CPO remains <0.6 operators should consider the following options:

- PAPI is <0.9 consider right sided hemodynamic support
- PAPI >0.9 consideration for additional hemodynamic support

Local practice patterns should dictate the next steps:

- Placement of more robust MCS device(s)
- Transfer to LVAD/Transplant center

If CPO is >0.6 and PAPI <0.9 consider providing right sided hemodynamic support if clinical suspicion for RV dysfunction/failure

Vascular Assessment

- Prior to discharge from the Cath Lab, a detailed vascular exam should be performed including femoral angiogram and Doppler assessment of the affected limb.
- If indicated, external bypass should be performed.

ICU Care

- Daily hemodynamic assessments should be performed, including detailed vascular assessment
- Monitor for signs of hemolysis and adjust Impella position as indicated

Device Weaning

Impella should only be considered for explantation once the following criteria are met:

- Weaning off from all inotropes and vasopressors
- CPO >0.6, and PAPI > 0.9

Bridge to Decision

Patients who do not regain myocardial recovery within 3-5 days, as clinically indicated, should be transferred to an LVAD/Transplant center. If patients are not candidates, palliative care options should be considered.

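### Appendix 1 guides Impella placement differently in its text and on its algorithm card when LVEDP is ≤15 mmHg and cardiac index is ≥2.2 or not measured

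*Protocol*

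**What the plan says.** The protocol's Appendix 1 contains a written algorithm in numbered sections and a one-page algorithm card.

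The written algorithm, section 1 (Confirmation of AMI Shock), defines shock as any two of three features: hypotension, end-organ hypoperfusion, and "Hemodynamic criteria represented by a cardiac index of < 2.2 L/min/m² or a cardiac power output ≤ 0.6 watts". Criterion 2c of the Registry Inclusion Criteria is the same.

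Section 2 (Access, Baseline Invasive Hemodynamics) first gives latitude: "any diagnostic steps to ensure the presence of AMI or CS are left to the discretion of the primary operator". It then says "If a right heart catheterization has not been performed prior to MCS placement we recommend measuring a LVEDP prior to placement of MCS", and for a low reading "In the event a LVEDP ≤ 15 mmHg, an alternate diagnosis should be suspected and right heart catheterization should be performed prior to MCS". The stated purpose of that catheterization is to confirm cardiogenic shock; the sentence names no confirming value.

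The card, under Access & Hemodynamic Support, says "Obtain either Fick calculated cardiac index or LVEDP" and then "IF LVEDP >15 or Cardiac Index < 2.2 AND anatomy suitable, place IMPELLA". CPO first appears on the card in the calculations after PCI.

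The Registry Inclusion Criteria require Impella support and set no LVEDP threshold. Appendix 2 asks joining hospitals to adopt the algorithm as their standard of care, allows deviation at the operator's discretion, and allows patients with deviations into the registry.

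**The concern.** Sites are asked to adopt one algorithm, but for some patients the two versions of it do not give the same next step. The text has a pathway for a low LVEDP: suspect another diagnosis, catheterize, confirm shock. The card has none. The text counts low cardiac power as evidence of shock before the device goes in; the card's trigger does not use it.

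This matters for the analysis because Impella support is itself an entry criterion. A patient who is not implanted because the card's trigger was unmet cannot enter the survival denominator. The Data Management section sends such a patient to the Patient Exclusion Form (Appendix 4), which has no survival field. If some of the roughly 75 planned sites work from the card and others from the text, they may select differently within this group, and adherence to the algorithm cannot be defined consistently.

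**Working it through.** The plan has no figure to reproduce here. The check sets the two versions side by side, then asks whether the disputed group can exist.

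**Step 1: compare the rules by measurement pattern.**

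- LVEDP >15: the text does not divert the patient, and the card's trigger is met (given suitable anatomy). They agree.
- LVEDP ≤15 and CI <2.2: catheterization under the text shows its hemodynamic criterion met, and the card's second arm is met. They agree.
- LVEDP ≤15, CI not measured: the text calls for right heart catheterization before support. On the card, LVEDP alone completes the measurement step, the trigger is unmet and no further step is given. They differ.
- LVEDP ≤15 and CI ≥2.2: the card's trigger is unmet. Under the text, shock can still be present by the two-of-three definition. They differ.

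**Step 2: list the shock patterns in the last group.** With LVEDP ≤15 and CI ≥2.2, four combinations meet two of three:

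1. hypotension and CPO ≤0.6 W;
2. hypoperfusion and CPO ≤0.6 W;
3. hypotension, hypoperfusion and CPO ≤0.6 W;
4. hypotension and hypoperfusion with CPO >0.6 W.

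Three of the four involve low cardiac power, the measurement missing from the card's trigger.

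**Step 3: can CPO be ≤0.6 W when CI is ≥2.2?** The card gives CPO as mean arterial pressure (MAP) times cardiac output, divided by 451. Cardiac output is CI times body surface area (BSA). Setting CPO to 0.6 and solving:

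MAP limit = 0.6 × 451 / (CI × BSA) = 270.6 / (CI × BSA)

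The protocol gives no BSA, so 1.7, 1.9 and 2.1 m² are assumed.

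- CI 2.2: 270.6 / 2.2 = 123.0. Dividing by BSA gives 72.4, 64.7 and 58.6 mmHg.
- CI 2.5: 270.6 / 2.5 = 108.24. Dividing by BSA gives 63.7, 57.0 and 51.5 mmHg.

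For scale, the card's hypotension line of 90/60 corresponds to a MAP of about (90 + 2 × 60) / 3 = 70 mmHg by the usual approximation. The limits at CI 2.2 lie near or below that, so a hypotensive patient can reach them. They fall as CI rises, so the pattern becomes harder to meet further above the cut-point.

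**Step 4: how many patients?** This cannot be computed. It needs the joint distribution of LVEDP, CI, MAP and BSA, and the documents give none of these.

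**The case against.** The strongest reply is that this is a summary card with a line missing. Both versions cut LVEDP at 15 mmHg. The card already lists a Fick cardiac index, and asking for either measurement does not bar taking both; if catheterization then shows CI <2.2, the card is satisfied. Operators have discretion, deviating patients can be entered, and the protocol describes itself as a registry and not a treatment study. Much of this stands and limits the point. It does not remove it: the card never calls for the second measurement, and the deviation clause cannot bring in a patient who was never given the device.

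Several stronger readings are tempting but unsupported.

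- A reader might infer that the card forbids Impella outside its trigger. It states when to place the device and does not say that these are the sole conditions.
- A reader might infer that the text confirms shock specifically by CI or CPO after a low LVEDP. That follows from the definition in section 1, not from the catheterization sentence.
- A reader might see a conflict over sequence, since the text leaves "timing of right heart catheterization, coronary angiogram and placement of MCS" to the operator while the card puts Impella before PCI and lists that as a quality measure. But the text's own sections also run from Impella insertion to intervention, and the protocol body tracks pre-PCI Impella as a metric.
- A reader might infer that unsupported patients vanish. They are meant to be logged on the Patient Exclusion Form, although without survival.
- A reader might estimate the share of patients who qualify on cardiac power alone. Such a share would be taken before any LVEDP restriction, and those with LVEDP >15 already meet the card's trigger.

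**Conclusion.** The inconsistency is real and narrow. Text and card give different guidance when LVEDP is ≤15 mmHg and CI is either ≥2.2 or not measured. They differ on two matters: whether CPO counts before placement, and what follows a low LVEDP. The arithmetic shows that the group with CI ≥2.2 and low cardiac power can exist at pressures a hypotensive patient may have. That rests on assumed BSA values and is most favourable at CI exactly 2.2. Its size is unknown.

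The documents do not support the broader claim that two different populations receive the device and enter the registry. What they support is that, within this group, sites following the card and sites following the text may differ in whom they support. Any effect on the survival denominator is indirect, limited by discretion and permitted deviations, and not quantified. It is still worth correcting, because sites adopt this algorithm as standard of care and the correction costs little.

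**What to change.** Reconcile sections 1 and 2 of Appendix 1 with the card's Access & Hemodynamic Support box, so that both say the same thing on whether CPO counts before Impella placement and on what follows an LVEDP of 15 mmHg or less. Which clinical rule applies is the sponsor's decision. The cost is a wording change to Appendix 1 and a re-issue of the card.

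Optionally, use the pre-Impella LVEDP, CI and CPO fields already on the case report form (Appendix 3) to classify entered patients by whether the text, the card or both would have supported placement. This is one derived variable. It has limits: the form allows catheterization after Impella or not at all, so pre-Impella CI and CPO may be missing, and no such classification can recover patients who were never implanted.

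### Appendix 1 gives inconsistent direction on right-sided support when post-PCI CPO is above 0.6 and PAPI is below 0.9, and its boundary values are not harmonised

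*Protocol*

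**What the plan says.** The algorithm appears twice in Appendix 1 of the Protocol, as numbered text and as a one-page card (v1.5, 11/2017).

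**Text, section 4 (Post-PCI Hemodynamics).**
- First paragraph: at CPO above 0.6, "no further intervention is required". At CPO of 0.6 or below, "right heart pressure will be reviewed to identify evidence of right ventricular failure if present (PAPi < 0.9").
- Second paragraph: "If evidence of right ventricular failure are present (PAPi < 0.9), or if the Impella is suctioning, operators should consider right ventricular support". This sentence carries no CPO condition. The paragraph continues "Irrespective of CPO, evidence of RV shock is a warning not" to increase alpha agonists.
- Third paragraph, on left-sided escalation, begins "If CPO < 0.6 persists and RV shock is not the cause".

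**Card.**
- The weaning branch needs CPO above 0.6 and PAPI above 0.9.
- The escalation branch opens with "If CPO remains <0.6 operators should consider the following options" and divides into PAPI below 0.9 and PAPI above 0.9.
- A further line reads "If CPO is >0.6 and PAPI <0.9 consider providing right sided hemodynamic support if clinical suspicion for RV dysfunction/failure".

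The definition of cardiogenic shock, in the registry inclusion criteria and in Appendix 1 section 1, counts CPO of 0.6 or below as meeting the hemodynamic criterion.

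**The concern.** An operator who follows the first paragraph of section 4 stops at CPO above 0.6, because the text calls for the right ventricular review only at or below that value. An operator who follows the second paragraph, or the card, treats PAPI below 0.9 as a reason to consider right-sided support in the same patient. The step concerns right ventricular failure, so an inconsistent instruction to sites is a patient-safety matter, if a modest one.

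It also touches interpretation. Under Appendix 2, hospitals that join adopt the algorithm as their standard of care, and the initiative hopes to show that such algorithms succeed. If the algorithm says two things about one group of patients, then for that group treatment according to the algorithm has no single meaning.

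**Working it through.** The plan states no figure to reproduce. The check sets the rules side by side and reads off what each says for CPO below, at and above 0.6, and PAPI below, at and above 0.9.

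**Inputs.** The text rules come from Appendix 1 section 4. The card rules come from its Wean OFF Vasopressors and Inotropes and Escalation of Support boxes. Two reading assumptions are made: the Impella is not suctioning (the text's other trigger for right ventricular support), and RV shock in the text's left-sided step means PAPi below 0.9.

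| CPO | PAPI | Text | Card |
|---|---|---|---|
| 0.5 | 0.8 | Review; consider RV support | Consider right-sided support |
| 0.5 | 0.9 | Review; consider left-sided escalation | Escalation opens, but neither PAPI sub-branch applies |
| 0.5 | 1.0 | Review; consider left-sided escalation | Consider additional support |
| 0.6 | 0.8 | Review; consider RV support | No branch |
| 0.6 | 0.9 | Review; no next step | No branch |
| 0.6 | 1.0 | Review; no next step | No branch |
| 0.7 | 0.8 | First paragraph: nothing further required. Second paragraph: consider RV support | Consider right-sided support if clinically suspected |
| 0.7 | 0.9 | Nothing further required | No branch |
| 0.7 | 1.0 | Nothing further required | Wean drugs; decide on device removal |

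**Step 1: the four combinations away from the boundaries.** At 0.5/0.8 and 0.5/1.0 text and card broadly agree. At 0.7/1.0 they are compatible, since weaning is not a further intervention in the sense of escalation. At 0.7/0.8 they diverge, and the text also diverges from itself.

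**Step 2: can the text be read so that the divergence disappears?** There are two readings of its second paragraph.
- If it applies at any CPO, it agrees with the card but sits against the first paragraph's statement that nothing further is required.
- If it applies only after the review at CPO of 0.6 or below, the text is consistent with itself but differs from the card.

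Either way one passage needs correcting. The remark that applies irrespective of CPO does not settle the matter, because it concerns alpha agonists and not device support.

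**Step 3: boundary values.** The text uses 0.6 or below to start its review but strictly below 0.6 for left-sided escalation. A CPO of exactly 0.6 without right ventricular failure is therefore reviewed and then left without a next step. The card uses only strict inequalities, so CPO of 0.6 has no branch, and PAPI of 0.9 matches neither PAPI condition at any CPO.

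**The case against.** The strongest defence is that the two instructions can both be followed. Saying that nothing further is required does not forbid right-sided support, and the card only asks that it be considered on clinical suspicion. Neither mandates or excludes a device. This stands as far as it goes: the difference is partly one of strength. It does not remove the point, because the text's first paragraph does not call for the right ventricular review above 0.6, while the card makes PAPI a decision variable there.

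A second defence is that the pathway does not truly end at CPO above 0.6. Section 2 plans PAPi during the index procedure at any CPO, section 4 obtains right heart pressures before the CPO branch, and both text and card require PAPI above 0.9 before explantation is considered. This also stands. The information is available in both versions, and explantation is handled consistently. The inconsistency is confined to whether right-sided support should be considered.

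On the boundaries, a reader might infer that the gap is wide because a CPO recorded to one decimal as 0.6 could be anything from 0.55 to 0.65. The documents do not support that: the case report form leaves the CPO cell blank and no section fixes a recording precision. As written, the gap is at exact equality and is a drafting point.

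**Conclusion.** The inconsistency is real and can be shown from the current text of Appendix 1 alone. One of the four CPO/PAPI combinations away from the boundaries (CPO above 0.6, PAPI below 0.9) has no single instruction. The unharmonised inequality signs are a minor addition. The conclusion rests only on the wording, with the two reading assumptions stated in the check. The documents do not say what share of patients fall in this group, so no frequency can be attached.

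A reader might infer that survival results or the figures on additional devices are compromised. The documents do not support this:
- The algorithm is voluntary, operators may depart from it, and patients with departures can be included (Appendix 2).
- No inclusion or exclusion criterion depends on this branch, and survival is ascertained in the same way whichever passage was followed.
- The case report form records post-PCI CPO and PAPI, the Impella type (including RP) and devices added after the index procedure, so the affected patients and their device use can be identified.

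A reader might also infer that sites work from competing versions of the algorithm. Text and card sit in the same appendix, and nothing shows sites choosing between them.

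What remains is a consistency correction of low severity. Its benefit is a clear instruction to sites on a right-ventricular-failure decision and one meaning for treatment according to the algorithm.

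**What to change.** The sponsor's clinical leads should reconcile the first and second paragraphs of Appendix 1 section 4 with each other and with the card's Escalation of Support box. Each combination of CPO (below, at, above 0.6) and PAPI (below, at, above 0.9) should carry one instruction, worded the same in both places. A table like the one in the check would show that every cell is filled. Which instruction belongs in each cell is a clinical decision on which no view is given here.

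The cost is a wording amendment to Appendix 1 and a reissued card with a new version number, sent to participating sites. Eligibility, the case report form, data collection and the planned number of patients do not change.
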